Eligible women will be invited to participate in the study. When recruitment is conducted in person, the care manager will make every effort to complete the consent process at that time, and she will also attempt to complete the 45-minute baseline structured interview, described below. If this is not possible, the care manager will schedule another appointment, as soon as possible, to conduct the baseline interview by phone or in person at the CHC. Based on prior collaborative care research with minority patients in these Bronx CHCs and other similar settings, we expect a consent rate of about 70%.^{76,99} In keeping with PCM and other collaborative care research,^{76,112} we will use a randomized block algorithm, stratified by CHC to assign women to the PCM control arm or the CCI intervention arm. Block size will be allowed to vary randomly to preclude any exercise of judgement, or bias, in the allocation of participants to specific arms. Study participants will be randomized 1:1 to each of the two arms, according to a scheme prepared by the study statistician, who is not onsite at any of the CHCs. Randomization will occur after the baseline interview; women in the study will be notified of their assignment at the time of the first call with the care manager. [name], study data coordinator, will disclose the block randomization process and will inform care managers of the assignments. [name], Project Director, will supervise [name] and all aspects of data collection described below.

Initial phone contact

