We will recruit 800 women to the study. To be eligible for the study, women must be patients at one of the six participating Bronx CHCs. They must also be between 50 and 64 years of age, speak English or Spanish, reside in the Bronx, screen positive for depression based on the PHQ-9 (≥ 8) at time of recruitment, and be out-of-adherence with current U.S. Preventive Services Task Force cancer screening guidelines for breast, cervical, and/or colorectal cancer screening. Women will be considered out of adherence if they have not received a Pap test without HPV in the past three years or a Pap test with HPV in the past five years, a mammogram in the past two years, and/or one of the following forms of colorectal screening: FOBT (or FIT) within the past year, flexible sigmoidoscopy in the past five years, or colonoscopy in the past 10 years. A woman who has had total hysterectomy is considered up-to-date for cervical cancer screening after the date on which the hysterectomy was performed.⁷⁶ We aim to be as inclusive as possible in this study. However, to maximize feasibility and in keeping with prior collaborative care research^{99,112}, we will exclude women who report the following when screened: terminal illness, current pregnancy (albeit unlikely in this age range), substance use, decisionally impaired or suicidal thoughts. We will exclude prisoners. Data received from the six health center sites support the availability of potential study participants and demonstrate the need for a study such as this one. In 2011, across the study sites, mammography rates for women 50-64 years of age were 56%, 57% and 64%; Pap testing rates were 62%, 50% and 53%. All of these rates fell substantially below the New York City target of 85% or greater. For colon cancer screening, rates in 2011 were 24%, 52%, and 27%, also much lower than the New York City target of 60% or greater. Additionally, depression rates for women of this age range in 2011 were 35% (including dysthymia), 21%, and 21%, which is consistent with the literature.

H. RECRUITMENT OF SUBJECTS

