Participating sites are Morris Heights Health Center, Urban Health Plan and Montefiore Primary Care Practice. We have added Segundo Ruiz Belvis and Morrisania Diagnostic and Treatment Centers and Lincoln Primary Care Practice as three additional sites. We will recruit approximately 800 women ages 50-64 who screen positive for depression and who are non-adherent with cervical, breast, and/or colorectal cancer screening guidelines from one of the participating Bronx sites. Women in this age range should receive all three types of cancer screening. We are focusing solely on women because estimates of depression among minority women in the Bronx are 20%-25%, at least twice that of men, and depression has been shown to be a barrier to screening, with consequences for cancer morbidity and mortality. Patients will be approached and screened in the participating sites in person or by phone to

determine whether they meet initial study inclusion criteria; they will have been identified as potentially eligible by the electronic medical record. Only patients who speak English or Spanish are eligible. For this screening, patients will provide verbal consent; the data will be anonymized. Patients will receive \$5 for their participation in the screening. If a patient confirms through this initial screening that she is out-of-adherence for one or more types of cancer screening (breast, cervical, and/or colorectal), the patient will be administered the Patient Health Questionnaire (PHQ)-9 to determine whether she meets criteria for depression. Those patients who score greater than or equal to 8 on the PHQ-9, do not have a terminal illness, are not pregnant, are not prisoners, are not decisionally impaired and are not active substance users will be asked to provide written informed consent to participate in the study. Patients will be told that study involvement entails speaking with a care manager at least once per month by phone or in-person, as they prefer, and they will be told about the two arms of the study and the randomization process. They will also be informed that participation will involve completing a baseline interview at the time of screening or within the week, as well as two follow-up interviews at 6 and 12-months after the baseline assessment.

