Colonoscopy) were compared separately between the two intervention arms using a chi square test comparing two independent binomial proportions (Aim 1). Next, logistic regression was used to control for potential confounders, including the factors discussed that were identified as being unevenly distributed between the CCI and PCM intervention arms at baseline. To account for possible differences by site, site indicators were included in the model as a fixed effect to examine if there were potential confounders; if they were not found to be confounders, they were removed from the model. A combined ordinal cancer screening outcome, calculated as number of up to date cancer screening tests (which vary from 0 to 3) was analyzed using the proportional odds model (PROC GENMOD in SAS). Other key patient-reported outcomes, including changes in depression, self-efficacy, stigma, satisfaction with cancer screening decision and satisfaction with care, and quality of life, were also compared between the two intervention arms (Aim 2). For continuous outcomes, a two-sample t-test was used to examine the difference between the two arms, and a linear regression model was used to control for potential confounders; for categorical outcomes, a chi-square test was used to examine the difference between the two arms and a logistic regression (for binary outcome) or a multinomial logistic regression (for a categorical outcome with more than two levels) was also used to control for potential confounders.

Multivariate analyses testing for moderators and mediators

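### Randomisation is stratified by CHC, but the first comparison ignores site and the model drops it unless it looks like a confounder: a small loss of precision and a model not fixed in advance

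*SAP*

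**What the plan says.** On design, Protocol section C (Study Procedures) states: "we will use a randomized block algorithm, stratified by CHC to assign women to the PCM control arm or the CCI intervention arm". It adds: "Study participants will be randomized 1:1 to each of the two arms". Section G (Study Subjects) puts the number of strata at six: "women must be patients at one of the six participating Bronx CHCs". Section H describes three of these "as three additional sites".

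On analysis, the SAP section Intention to treat (ITT) analysis compares cervical, breast and colorectal screening separately, "using a chi square test comparing two independent binomial proportions". Site plays no part in that test. Logistic regression follows, with site indicators as fixed effects to see whether site confounds the comparison; "if they were not found to be confounders, they were removed from the model". The SAP does not define what would count as a confounder. Its descriptions of the proportional-odds model for the number of up-to-date tests, and of the t-tests, chi-square tests and regressions for the other outcomes, do not mention site. Neither document says that site is kept because it was the stratification factor.

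**The concern.** A confounder must be associated both with the outcome and with treatment arm. Blocked 1:1 allocation within each CHC removes the second association by design. A rule that keeps site only if it confounds therefore tends to remove it, even where site predicts screening well. The reason to keep site is different: it was a randomisation stratum, and it may be prognostic.

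Two things are at stake. First, stratified blocking removes between-site variation from the true sampling error of the arm difference, but an unstratified test still charges for it. Taken alone, this makes the test conservative and the risk-difference interval too wide. Second, an undefined keep-or-drop step means that the adjusted model is settled only after the data are seen.

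**Working it through.** **1. The plan's own power figure.** SAP, Sample size/Power Calculation: 356 per arm, about 80% power, 10-point difference, two-sided 5%. The control rate is not given as a number. With n = [z(α/2)·√(2p̄q̄) + z(β)·√(p1q1 + p2q2)]² / Δ² and rates of 30% and 40%:

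- (1.960 × √0.455 + 0.8416 × √0.450)² / 0.01 = 356.

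The figure reproduces at a control rate of 30% (or 60%). Over control rates from 20% to 70%, power with 356 per arm runs from 76.2% to 87.1%.

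**2. Between-site share of variance.** Inputs: the 2011 rates in Protocol section G. That section speaks of six sites but lists three figures per test. Assumption: equal-sized sites with this spread. Share = variance of site rates / [p̄(1 − p̄)].

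- Colorectal (24%, 52%, 27%): p̄ = 0.343; 0.01576 / 0.2254 = 7.0%.
- Pap test (62%, 50%, 53%): p̄ = 0.55; 0.0026 / 0.2475 = 1.0%.
- Mammography (56%, 57%, 64%): p̄ = 0.59; 0.00127 / 0.2419 = 0.5%.

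**3. Effect on the standard error (SE) of the risk difference.** Inflation = 1/√(1 − share): 1.037 for colorectal (3.7% too large), 1.005 for Pap and 1.003 for mammography.

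**4. True type I error of the unstratified test.** 2 × [1 − Φ(1.96 × inflation)] = 4.2% for colorectal and 4.9% for each of the other two.

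**5. Power, colorectal, starting from a nominal 80%** (2.8016 = 1.9600 + 0.8416).

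- Unstratified: Φ[(2.8016 − 1.9600) × 1.0369] = Φ(0.873) = 80.9%.
- Site kept: Φ(2.8016 × 1.0369 − 1.9600) = Φ(0.945) = 82.8%.
- Gain: 1.9 points. For the unstratified test to match it, the sample must grow by a factor k with 2.8016√k − 1.9600 = 0.945/1.0369. This gives √k = 1.0249 and k = 1.0504, so 712 × 0.0504 = about 36 women.

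**6. Simulation check.** 200,000 trials per scenario, 356 per arm, six sites balanced by arm, each 2011 rate used for two sites.

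- Colorectal, no effect: mean reported SE 0.0355 against a true sampling SD of 0.0343; rejection 4.3% unstratified, 5.0% Cochran-Mantel-Haenszel (CMH).
- Power for a 10-point effect, unstratified against CMH: colorectal 79.2% and 81.2%; Pap 78.3% and 78.4%; mammography 79.6% and 79.7%.

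**7. Sensitivity.** If the three added sites lie at the mean, the colorectal share halves to 3.5%. The SE is then 1.8% too large, true type I error is 4.6%, and the power gain is about 1 point.

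**8. Logistic model, colorectal, 10-point effect.** Without site, the log odds ratio is 0.422 with reported SE 0.155 (true SD 0.149). With site, it is 0.453 with SE 0.161. The reported SE rises, but the ratio of estimate to SE goes from 0.422/0.155 = 2.72 to 0.453/0.161 = 2.81.

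**The case against.** The strongest reply is that the loss is slight and its size uncertain. The 2011 rates are clinic-wide figures from three of six sites. Trial participants are depressed and already overdue for at least one test, and the outcome follows a year of care management in both arms. The colorectal share comes from one outlying site on one of three outcomes. All of this stands, and it is why the figures are illustrative only.

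Four stronger readings are tempting, and the documents do not support them.

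- *Power rises from 80% to 83%, or 712 women behave like about 765 (712/0.930).* This sets the nominal calculation against the stratified test. The blocking also lowers the true sampling error of the unstratified test, whose actual power is 80.9%. The gain is about 2 points.
- *Deleting the rule would narrow the odds-ratio intervals.* It would not (step 8). Too wide describes the risk difference.
- *The trial's tests are conservative overall.* Protocol section B (Care Managers and Intervention Delivery) has two half-time care managers per CHC, one of them for CCI. Clustering by care manager is a separate matter that could make the SEs too narrow. With 12 site-by-arm clusters of 712/12 = 59.3 women, an assumed intraclass correlation of 0.001 to 0.01 multiplies the SE by √(1 + 58.3 × ICC) = 1.03 to 1.26. The net direction is unknown.
- *Site is certain to be removed.* The SAP gives no criterion, and its complete-case exclusions (Missing Data) could disturb the balance. Removal is likely, not assured.

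**Conclusion.** The mismatch between design and analysis is real, and its consequence is modest. The first-listed test omits the only stratification factor that the Protocol names, and the removal rule asks the wrong question of it. Considering the site effect alone, and on the equal-size and 2011-rate assumptions, the cost for colorectal screening is an SE about 3.7% too large and about 2 points of power; it is smaller if the added sites lie near the mean. For the other two tests the cost is negligible. The omission does not bias the arm comparison or inflate type I error, so it does not invalidate the result. The undefined, data-dependent choice of model remains a fault whatever the power gain.

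**What to change.** Delete the removal rule. Make the per-test comparison a CMH test stratified by CHC, reported with a stratified risk difference and its interval. Keep site indicators in every logistic, linear and proportional-odds model, whatever imbalance is observed.

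The cost is five degrees of freedom (six sites less one) and a re-run, with no new data. The SAP is written in the past tense and already reports a baseline comparison, so this may be more than a change of wording. If the analysis has been run, present the stratified results as a labelled re-analysis beside those already obtained. A by-site forest plot is optional and not part of the correction.

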Statistical Analysis Plan

Collaborative Care to Reduce Depression and Increase Cancer Screening among Low-Income Urban Women

NCT Number: 02273206

Document Date: July 30, 2017

**Collaborative Care to Reduce Depression and Increase Cancer
Screening among Low-Income Urban Women – Prevention Care Manager 3 Project**

Statistical Analysis Plan

Overview

The primary analysis was based upon the intention-to-treat (ITT) approach, with data from each participant analyzed as per initial assignment to one of the two intervention arms. Our analysis proceeded in several steps: 1) data checking to identify and resolve the reasons for missing values, inconsistencies, and out-of-range values; 2) descriptive analyses of the baseline characteristics of the two intervention arms; 3) formal comparison of participation in screening tests and changes in depression between the CCI intervention and PCM controls arms, intention-to-treat analyses, per protocol analyses, and analyses that accounted for missing data; and 4) multivariate analyses testing for moderators and mediators.

Data checking and descriptive analysis

Data analysis was preceded by intensive data checking to identify and resolve the reasons for missing values, inconsistencies, and out-of-range values. Summary statistics describing the baseline characteristics of each intervention arm are presented, including age, primary language, marital status, health insurance, smoking status, body mass index, medical history, family history and comorbid conditions, etc. Continuous variables were summarized using means and standard deviations, while categorical variables were summarized using proportions with cut points made for median or quartiles as appropriate. A comparison of the distribution of baseline characteristics was made between the two intervention arms. There were no differences between the two groups with respect to their distribution by baseline characteristics. In addition to the baseline characteristics, we tabulated the study endpoints of interest, the extent of dropouts, and protocol violations for each intervention arm separately.

Intention to treat (ITT) analysis

Data from each study subject were analyzed as per initial assignment to the intervention arm. First, completion of cervical cancer screening (Pap test), breast cancer screening (mammogram), and colon cancer screening (HFOBT/FIT, Barium Enema, Sigmoidoscopy or

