To determine whether reducing depression increases the likelihood that low-income women will receive age-appropriate cancer screening (Aim 3), we included improvement in depression (as well as depression remission in a separate model) in the logistic regression models to examine its association with cancer screenings, and also to examine if the difference between the two intervention arms was modified by change in depression; we examined the interaction between improvement in depression and treatment (as well as depression remission and treatment). To determine whether the effectiveness of the CCI intervention varies according to patient characteristics, such as language spoken and, obesity, etc. (Aim 4), we examined each of these variables as possible effect modifiers. However, it is understood that the statistical power for testing an interaction term may be limited in this study; consequently, this aim was treated as exploratory and the results of this study will be used to design a future, more definitive study with interventions identified and targeted to address issues associated with specific subgroups who may experience reduced benefit from the intervention.

Missing Data

Missing data are a common problem in longitudinal studies. In the context of the present study, missing data will occur when, for example, not all the screening outcomes are reported for a given participant, or some of the co-variables (e.g., body mass index) are missing. For the initial approach in the primary analysis of the study, study participants with missing values on either the outcomes or the co-variables were first removed from the study for the evaluation of intervention effects. However, this approach required the assumption of missing completely at random to be true. A violation of this assumption may lead to bias in the estimate of the intervention effect. We first examined the level of missing data by each outcome and each co-variate in the model. If the rate of missing data is small (<5%), the chance that it will bias the result is very low; however, if the rate of missing data is moderate (>10%), sensitivity analysis was used to examine the robustness of the result. For example, if one variable has a moderate level of missing, we conducted a sensitivity analysis which compared those participants with the remaining participants and also included those participants in the analyses by adding a separate missing category.

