Heterogeneity of Treatment Effects (HTE) Analysis

A potential problem in intervention studies is heterogeneity within the participant population. To examine whether the effectiveness of intervention varies according to patient characteristics, here we focused on BMI and primary language as previous evidence supported that these two characteristics affected the likelihood of being up to date with cancer screening. In addition, because women who were up to date at baseline may be very different from women who were not up to date at baseline, we examined the subset of women who were not up to date for each specific cancer screening and examined if the intervention improved their up to date screening status.

Sample size/Power Calculation

The primary aim of the study was to compare the effectiveness of the Collaborative Care Intervention (CCI) versus Prevention Care Management (PCM) to increase participation in screenings for cervical cancer, breast cancer and colon cancer among women with depression. Women were equally randomized to the two intervention arms. With 356 women in each arm, the study had about 80% power to detect a minimum 10% difference between two arms in cancer screening participation with a two-sided type I error rate of 5%, under various assumptions of screening rate for the PCM (control) group. This 10% difference is considered the smallest difference of interest, based on previous studies comparing the PCM to Usual Care.^{1, 2,3} Therefore, with 356 women with complete data per intervention arm (n=712) our study had sufficient power to detect a clinically meaningful difference between the two intervention arms.

Multiple Comparisons

We evaluated three separate screening outcomes (for cervical cancer, breast cancer and colorectal cancer) so that multiple hypothesis testing would be involved. However, the relative importance of factors contributing to participation in each screening test varied between tests, and we were interested in comparing the two intervention arms for each test separately, as well as globally for all three tests. We also examined a summary of cancer

screening outcome across three types of cancers by comparing the total number of up to date cancer screenings at the follow-up between the two treatment arms, using a regression model for ordinal outcome. Since these statistical tests were hypothesis-driven rather than exploratory, we did not think multiple comparison adjustment for type I error rate was necessary.

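### Aim 3 asks whether reducing depression raises screening, but the SAP relates non-randomized improvement to screening without a fixed visit or instrument and without naming the baseline factors that most need adjustment

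*SAP*

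**What the plan says.** The SAP section on moderators and mediators opens: "To determine whether reducing depression increases the likelihood that low-income women will receive age-appropriate cancer screening (Aim 3), we included improvement in depression", with remission in a separate model, "in the logistic regression models to examine its association with cancer screenings". It then asks whether the arm difference depends on change in depression: "we examined the interaction between improvement in depression and treatment (as well as depression remission and treatment". Separately, the ITT section compares depression by arm: "Other key patient-reported outcomes, including changes in depression". The public SAP does not combine that comparison with the depression-to-screening association into an indirect effect.

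On adjustment, the ITT section controls for "potential confounders, including the factors discussed that were identified as being unevenly distributed between the CCI and PCM intervention arms at baseline", and for site if site proves to be a confounder. The data-checking section reports: "There were no differences between the two groups with respect to their distribution by baseline characteristics".

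Protocol section F defines improvement as a reduction of more than 50% on the SCL-20 or PHQ-9, and remission as SCL-20 below 0.5 or PHQ-9 below 5. Interviews are at baseline, 6 and 12 months (section C). Entry needs PHQ-9 of at least 8 and one overdue test (section G). The Main Hypotheses text in section B expects CCI to raise screening through lower depression. It concedes that change is not linear and leaves any look at the reverse direction to unspecified exploratory work.

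**The concern.** Randomization balances CCI against PCM. It does not balance women who improve against women who do not, so a search for imbalance between arms cannot find the factors that distort the improvement-screening association. Two obvious candidates are not named for Aim 3.

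- **Baseline depression.** Remission is a fixed threshold, so it depends on the entry score.
- **Baseline up-to-date status for the test being analyzed.** One overdue test is enough for entry, so a woman can already be current for the other two. The SAP recognizes this in its heterogeneity section, "because women who were up to date at baseline may be very different from women who were not up to date at baseline", but uses the restricted subset only where it "examined if the intervention improved their up to date screening status".

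Time order is also open. If the 12-month score is used, a test done in month 3 can precede the improvement said to explain it.

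The report could therefore conclude that reducing depression raises screening when the two only share baseline causes, or when screening came first. The conclusion would be used: section B presents the trial as a test of whether reducing depression is a necessary step, and the SAP's exploratory label is attached to Aim 4, not Aim 3.

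**Working it through.** **The plan's own figure.** The only power statement is for the comparison of arms: 356 per arm, 10-point difference, two-sided 5%, about 80%. With n = [1.96·√(2·p̄·q̄) + 0.8416·√(p₁q₁ + p₂q₂)]² / (p₂ − p₁)² and 30% against 40%, n = (1.96·√0.455 + 0.8416·√0.45)² / 0.01 = (1.3221 + 0.5646)² / 0.01 = 356. It reproduces. It does not cover Aim 3.

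**Set-up.** All runs use 356 per arm, arm in every model, no effect of depression on screening, two-sided 5% and 4,000 simulated trials (simulation error up to about 1.5 points). Odds ratios (ORs) come from 1,000,000 simulated women. The association strengths are assumptions; the documents give none.

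**1. Baseline screening status B left out.** logit P(improve) = −0.8 + ln(OR)·B + 0.5·arm. P(up to date at 12 months) = 0.9 if B = 1 and 0.4 if B = 0.

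| Share up to date at entry | Assumed OR, B to improvement | OR for improvement | Falsely significant |
|---|---|---|---|
| 20% | 1.2 / 1.5 / 2.0 | 1.07 / 1.14 / 1.25 | 6.5 / 12.9 / 31.5% |
| 50% | 1.2 / 1.5 / 2.0 | 1.10 / 1.26 / 1.45 | 8.8 / 28.5 / 66.4% |
| 60% | 1.2 / 1.5 / 2.0 | 1.11 / 1.25 / 1.47 | 9.6 / 26.0 / 65.6% |

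With B in the model the OR is 0.99 to 1.01 and rejection is 4.2% to 5.2%.

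The 2011 rates in protocol section G show whether such shares are plausible. Among women with at least one overdue test, the share current for a given test is (rate − all)/(1 − all), where all is the share current for all three. If tests are independent, all = 0.56 × 0.62 × 0.24 = 0.083 for the first-listed rates, and the mammogram share is (0.56 − 0.083)/(1 − 0.083) = 52%. Across the three sets of rates:

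- independent tests: mammogram 50–60%, Pap 41–59%, colorectal 17–44%;
- maximal overlap (all = the lowest of the three rates): 14–51%, 0–50% and 0–4%.

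This assumes that the rates are listed in the same site order, that they apply to depressed women, and that three sites' rates represent six.

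**2. Baseline severity left out.** Baseline PHQ-9 is normal(14, 4.5) truncated to 8–27 (mean 14.8, SD 3.8). Follow-up = 0.55·(baseline − mean) + mean − 4 − 1·arm + N(0, 4.5), clipped to 0–27. Screening has OR 0.9 / 0.8 / 0.7 per SD of baseline.

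- Remission model: OR 1.09 / 1.17 / 1.28, significant in 6.8 / 11.2 / 20.5%. With baseline PHQ-9 added: OR 1.00 to 1.01, 4.4% to 5.0%.
- Improvement model (more than 50%): OR 1.01 to 1.02, significant in 4.6% to 4.9%. It is hardly affected.

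**3. Screening before the 12-month score.** P(screen) = 0.45, a share e of it occurs early, and early screening raises later improvement by OR 1.25 / 1.5 / 2.0.

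- e = 30%: OR for improvement 1.07 / 1.13 / 1.24, significant in 7.7 / 12.1 / 28.4%.
- e = 50%: OR for improvement 1.11 / 1.23 / 1.42, significant in 11.4 / 26.3 / 61.3%.

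**4. Open choices.** Two instruments and two visits give 2 × 2 = 4 versions of each model. If the most favourable were reported, the false-positive rate would be 9.4% to 17.4% for correlations of 0.9 down to 0.3 between versions.

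**5. Interaction.** In CCI follow-up calls, screening waits for mental health barriers to be addressed unless the woman raises it (protocol section C). Letting that order link improvement and screening in CCI alone gives an improvement OR of 1.03 to 1.32 within CCI and a significant interaction in 4.5% to 13.0%.

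**The case against.** The best defence is that the SAP calls the result an association, so its method claims no causal effect. That is true, and it limits the point to a mismatch between the question and the analysis. The stated purpose is still to find out whether reducing depression increases screening, and this association does not answer that.

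Several stronger readings are tempting and not supported:

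- **That the SAP rules out adjustment for baseline severity or screening status.** Its confounder clause is open-ended and treats site separately. What is shown is that these factors are not named for Aim 3.
- **That the plan ignores the reverse direction.** The protocol acknowledges it, without specifying an analysis.
- **That no mediation plan exists.** The protocol's reference list includes a paper on mediation methods, and no public analysis text applies it. One can say only that the public SAP defines no indirect effect.
- **That the SAP passes off the arm-by-improvement interaction as baseline effect modification.** It does not; patient characteristics are handled separately under Aim 4. The interaction is simply not a mediation test.

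It is also fair to object that the larger error rates rest on assumed strengths. No passage shows that women current at entry improve more, or that screening leads to later improvement. At the weakest strengths used, the error rate is 6.5% to 11.4%.

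**Conclusion.** The point holds for Aim 3 as publicly specified. A causal question is addressed with a non-randomized exposure, no named adjustment for baseline depression or baseline up-to-date status, and no fixed visit or instrument. With no true effect and the assumed strengths above, the improvement term is falsely significant in 6.5% to 66.4% of trials through baseline screening status, and in 7.7% to 61.3% through screening that precedes the 12-month score. Baseline severity matters for the remission model and hardly at all for improvement of more than 50%. These figures show direction and possible size; they do not estimate the error in this trial.

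A reader might infer that any significant improvement term would be spurious, or that the trial's main results are in doubt. Neither follows. Where depression truly affects screening, a significant term is correct. The ITT comparisons, including depression by arm, and the sample size are untouched. The change should be made, but it concerns what can be concluded from Aim 3 only.

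**What to change.** In the Aim 3 models:

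1. Use change from baseline to 6 months on one named instrument. Keep the other instrument and the 12-month score as sensitivity analyses.
2. Adjust for baseline PHQ-9 or SCL-20, baseline up-to-date status for the test in question, GAD-7, prior mental health use and site.
3. Where the medical record gives screening dates, add a sensitivity analysis that counts only screening after the 6-month measure, among women still overdue then.
4. Report an adjusted association, not evidence that reducing depression raises screening. Do not read the arm-by-improvement interaction as a mediation test.

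An indirect effect, with stated assumptions and a sensitivity analysis for unmeasured confounding, is optional and exploratory. It would be imprecise. An assumed effect of 1.0 percentage point (improvement 31% against 41%, times 10 points) has a 95% sampling range of 0.1 to 2.2 with all 712 women. The range is −0.4 to 2.9 if the depression-to-screening path uses only 30% of them. It is also not identified if CCI call order is a post-randomization common cause of improvement and screening.

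Cost: items 1, 2 and 4 use measures already planned. The SAP is written in the past tense, so they mean reanalysis and rewording. Depression change in months 6 to 12 leaves the main model, and missing 6-month interviews cost precision. Item 3 depends on dates that the documents do not promise: self-report is yes/no, and section F describes record review at three centers although six sites take part. It also uses a post-randomization subset, so contrasts between arms within it are not randomized.
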